4.6 Study Days

Study day is defined as the number of days since first dose of IMP and, for a particular date, and is calculated as:

Study day = Assessment date – Date of first dose of IMP + 1, if date of assessment is on or after date of first dose of IMP

or

Study day = Assessment date – Date of first dose of IMP, if date of assessment is prior to the date of first dose of IMP

Therefore, the date of the first dose of IMP will be Day 1.

In the situation where the assessment date is partial or missing, Study Day, and any corresponding durations will appear partial or missing in the listings.

4.7 Definition of Baseline Values

The baseline value is defined to be the last non-missing assessment prior to randomization. For baseline WHO ordinal scale, if not collected prior to randomization, the earliest collected WHO ordinal scale collected on the same day as randomization will be used as baseline. Pre-randomization assessments on the same day as randomization will be considered the baseline assessment for each of these respective study procedures. Unless otherwise specified, change from baseline calculations for a treatment window assessment will be the applicable treatment window assessment minus the

baseline assessment. If either the treatment window assessment value or the baseline value is/are missing, then change from baseline will be set to missing.

Age in years will be calculated as (date of informed consent – January 01 of year of birth) / 365.2425.

4.8 *Planned Analyses*

The following statistical analyses are planned for this study:

- Unblinded safety analyses for Data Monitoring Committee (DMC): An independent DMC will be utilized throughout the study to monitor patient safety. DMC meetings for safety will be conducted after 33, 100, and approximately 208 subjects complete assessments through the 28-day follow up (Day 28), approximately 14 days after the final dose of study drug. A DMC charter will be developed preceding study initiation and will define DMC processes and meetings, and required report contents.
- Interim analysis: An interim look for safety and primary endpoint will be conducted by the DMC when approximately 208 patients in the ITT population complete assessments through the 28-day follow up (Day 28), approximately 14 days after the final dose of study drug.

When all subjects enrolled under the targeted or adjusted sample size have completed the study through Day 28 (i.e., full study enrolment is completed), the clinical database will be cleaned, frozen, and an assessment of the primary efficacy endpoint and secondary, exploratory, and safety endpoints up to Day 28 in the ITT population will be created. Individuals involved with the conduct of the study will not have access to unblinded data until database lock. Final analysis: final analysis on efficacy and safety will occur after the database is locked.

4.9 *Multiple Comparison/Multiplicity*

No multiplicity adjustment is planned.

5 Study Population and Disposition

5.1 *Analysis Population*

The number and percentage of patients in each analysis set as defined in [section 3](#) will be presented overall and by randomised treatment. The denominators for percentages will be based on the number of enrolled patients by randomized treatment and overall.

Overall patient status will be provided in a data listing, containing analysis population assignment, randomized treatment, actual treatment, date of consent, date of first dose, date of termination.

5.2 *Patient Disposition*

The number and percentage will be presented by randomized treatment and overall for:

- patients screened, randomized
- patients completing the study drug treatment
- patients completing the study
- patients who prematurely discontinued study drug treatment
- patient who prematurely withdrew from the study

QMS Document Name: Statistical Analysis Plan	Page 15 of 27
QMS No (include version ref): STF-015-GL.02	Document date: 09JUL2019
CONFIDENTIAL	

- reason for discontinuation of study drug treatment
- reason for withdrawing from the study as recorded in eCRF

The denominators for percentages will be based on the number of patients in ITT by randomized treatment and overall, except for patients screened and patients randomized.

Discontinued patients will be provided in a data listing by patient.

5.3 *Protocol Deviations*

Major protocol deviations will be judged by clinical/biostatistical study personnel prior to database lock.

Major protocol deviations may include but not limited to followings:

- Deviations of inclusion and exclusion criteria
- Receiving the wrong study intervention
- Non-compliance with study intervention defined as the participant taking < 80% of the study intervention through their last day of dosing.
- Taking a prohibited medication
- Other

The number and percentage of patients with major deviations will be summarized. The number of deviations by type of deviation will be summarized by treatment and overall. The denominators for percentages will be based on the number of patients in ITT population by randomized treatment and overall.

All protocol deviations (both major and minor) will be provided in a data listing by patient.

5.4 *Inclusion/Exclusion Criteria*

Inclusion and exclusion criteria deviations will be provided in a data listing by patient.

6 Demographics and Disease Characteristics

6.1 *Demographics and other baseline characteristics*

The following demographic characteristics will be summarized by treatment group and overall for patients in ITT population using descriptive statistics. No statistical hypothesis tests will be performed.

- Sex (male, female)
- Age (years)
- Age group (50 to < 75, ≥ 75 years)
- Race (American Indian or Alaska Native, Asian, Black or African American, Native Hawaiian or other Pacific Islander, White, Unknown, Other)
- Ethnicity (Hispanic or Latino, not Hispanic or Latino, not reported, unknown)
- Weight (kg) at baseline
- Height (cm) at baseline

QMS Document Name: Statistical Analysis Plan	Page 16 of 27
QMS No (include version ref): STF-015-GL.02	Document date: 09JUL2019
CONFIDENTIAL	

- BMI (kg/m²) at baseline
- SARS-CoV-2 (COVID-19) history
- PGD2 result at baseline
- Virus serology result of presence of HIV, Hepatitis B surface antigen (HBsAg), and HCV antibody if collected in eCRF.

Demographics and other baseline characteristics will be provided in a data listing by patient.

6.2 Medical History

The medical conditions are coded according to Medical Dictionary for Regulatory Activities (MedDRA® version 23.1) and will be classified as follows:

- Previous medical conditions, if medication is not “Ongoing at study entry” as indicated in CRF
- Concomitant medical conditions, if medication is “Ongoing at study entry” as indicated in CRF

The frequency and percentage of medical conditions recorded from medical history will be presented after classification into previous and concomitant conditions by system organ class (SOCs) and preferred terms (PT) by randomized treatment and overall. If patients have more than one disease within an SOC or PT, they will be counted only once for the respective SOC or PT.

The denominators for percentages will be based on the number of SAF by treatment group and overall.

7 Exposure and Compliance

7.1 Extent of Exposure

Duration of study drug exposure, defined as the number of days between the date of first dose following randomization and the date of the last dose, will be summarized by treatment group and over for the patients in SAF.

Duration will be calculated as date of last dose – date of first dose + 1.

If the date of first intake of IMP is missing, it will be assumed to be identical to the date of randomization.

7.2 Compliance

Compliance will be calculated and summarized by treatment group and overall. Compliance will be calculated as $100 \times (\text{total number of tablets taken} / \text{total number of tablets expected to be taken})$. The number of tablets taken will be derived as the number of tablets dispensed minus the sum of the number of tablets returned and the number of tablets reported lost/missing based on the CRF reported doses taken in hospital and the dose log. The percent compliance will be summarized. Summaries will be presented for SAF.

A listing of drug accountability will be presented for all medication distributed to each patient, including number of tablets dispensed, returned, lost/stolen, taken, and overall percent compliance.

8 Prior and Concomitant Medication

Prior and concomitant medications are coded according to the World Health Organization drug dictionary (WHO-Drug version MAR, 01, 2019) and stored with ATC codes and generic names.

QMS Document Name: Statistical Analysis Plan	Page 17 of 27
QMS No (include version ref): STF-015-GL.02	Document date: 09JUL2019
CONFIDENTIAL	

Medication will be classified as prior if the stop date and/or time was before the first dose of IMP. All other medications are defined as concomitant. Missing or partly missing stop dates will be imputed using the rules defined in [Section 4.4](#).

The number and frequency of previous and concomitant medications will be given per ATC level 2 and preferred term by treatment and overall. If a patient has received more than 1 drug within an ATC class/preferred term, he/she will be counted only once for the ATC class/preferred term.

9 Prior and Concomitant Procedure

Procedure will be classified as previous if the stop date and/or time was before the first dose of IMP. All other procedures are defined as concomitant. Type of procedure (prior or concomitant) and indication of procedure will be summarized. All summaries will be presented by dose cohort and overall.

Prior and concomitant procedure information will also be provided in a data listing.

10 Efficacy

10.1 Primary efficacy analysis

The number and percentage of patients who have died or have progressed to RF through Day 28 will be presented by treatment. Hypothesis test comparison of proportion between treatment will be analyzed using a logistic regression with predefined covariates and treatment group. The predefined covariates are region and age group. Other covariates including previous COVID-19 therapy may be explored as exploratory analyses. Estimation of the covariate-adjusted risk difference will be reported using Cochran-Mantel-Haenszel (CMH) weighting and estimates from the logistic regression as described by Ge and colleagues (Ge et al., 2011, Appendix C). Two-sided p-value of global test comparison between active and placebo will be reported. Odds ratio of each covariate and two-sided 95% CI will also be reported. This analysis will be repeated without the covariates.

The denominator for the proportions alive and RF-free at Day 28 will include all randomized subjects.

Time from date of randomization to death or first RF through Day 28, whichever comes first, will also be displayed using the Kaplan-Meier estimator and analyzed using a proportional hazards model analysis with the same covariates. If a patient doesn't have documented death or RF, it will be censored at the Day 28. For subject who discontinued study before Day 28 without documented outcome, it will be censored at the date of discontinuation. This analysis will be repeated without the covariates. Test statistics will be the Hazard Ratio with 95% CIs and p-values. Sensitivity test will be done using a Fishers Exact Test.

Primary endpoint will be analyzed using ITT, mITT, PPS (if formed) analysis set under randomized treatment.

Primary endpoint analysis will be repeated for subgroups as specified [section 4.3](#).

Sensitivity analysis and handling of missing primary endpoint data

If $\leq 5\%$ of subjects lack sufficient data to confirm the primary endpoint, four sensitivity analyses will be performed on logistic regression: 1) treat any missing primary outcomes as successes; 2) replaces

QMS Document Name: Statistical Analysis Plan	Page 18 of 27
QMS No (include version ref): STF-015-GL.02	Document date: 09JUL2019
CONFIDENTIAL	

any missing primary outcomes as failures; 3) missing primary outcome imputed as success for drug and failure for controls; 4) missing primary outcome imputed as failure for drug and success for controls.

If more than 5% of subjects have insufficient data to confirm RF-free and alive at Day 28, BioAge will employ a MI strategy (SAS MI, MIANALYZE) with missing at random (MAR) based protocol stratification factors (age and region), treatment, and the discharge status prior to or on Day 28. Following steps will be followed for multiple imputation.

Step 1: which will be carried out to produce n (exp. 25) imputed datasets

The SAS procedure PROC MI using the FCS (fully conditional specification method) statement with LOGISTIC imputation method to impute RF28 assuming no covariate will be missing.

One must also specify a VAR statement with outcome variable being the last in the order. If any covariate is expected to have missing and need to be imputed as well

`"LOGISTIC (RF28SUB_MI=TRT01P REGION AGEGRN DISC28)"` also need to be added after the FCS statement.

```
PROC MI DATA=RF28 _ DATA SEED=1305417 NIMPUTE=25 OUT=OUTLOG;  
  CLASS RF28 TRT01P REGION AGEGRN DISC28;  
  VAR TRT01P REGION AGEGRN DISC28 RF28;  
  FCS LOGISTIC (RF28SUB_MI=TRT01P REGION AGEGRN DISC28) ;  
RUN;
```

Where:

RF28 is respiratory failure or death prior to or on Day 28

TRT01P is randomized treatment (Placebo/Asapiprant)

REGION: region of patient's location (North America/South America)

AGEGRN: age group (50 - <75, >=75)

DISC28: discharge status prior to or on Day 28

Step 2: Each of 25 complete data set will be analyzed using standard logistic analyses as specified for primary efficacy analysis in SAP, i.e. PROC LOGISTIC will be used for RF28 with predefined covariates (region and age group) and treatment group.

```
PROC LOGISTIC DATA=OUTLOG ;  
  CLASS RF28 TRT01P REGION AGEGRN ;  
  MODEL RF28=TRT01P REGION AGEGRN / COVB;  
  BY IMPUTATION ;  
  ODS OUTPUT PARAMETERESTIMATES=LGSPARMS;  
RUN;
```

Step 3: The results logistic regression from the 25 complete data sets are combined for the parameter inference (i.e. coefficient estimate, 95% confidence interval, and p-value) using PROC MIANALYZE

```
PROC MIANALYZE PARMs=LGSPARMS;  
  MODELEFFECTS INTERCEPT TRT01P REGION AGEGRN;  
RUN;
```

QMS Document Name: Statistical Analysis Plan	Page 19 of 27
QMS No (include version ref): STF-015-GL02	Document date: 09JUL2019
CONFIDENTIAL	

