### 7.2.6 O2 Saturation/FiO2

The O2 saturation/FiO2 ratio will be collected on the study days as specified in [Table 1](#).

Oxygen saturation will be documented as a representative value at approximately the same time daily and will use a finger pulse oximeter to approximate O2 saturation.

FiO2 values will be obtained at the corresponding time to the O2 saturation values daily. If a subject is receiving supplemental O2 using a device that reports FiO2 values, then the FiO2 value will be reported from the device and recorded in the CRF. However, if there is no FiO2 readout available (e.g., subject is receiving supplemental O2 by nasal prongs), the site will record the method of O2 delivery and the flow rate in liters of O2 per minute (L/min) in the CRF. If the subject is breathing room air, this will be captured in the CRF rather than the O2 delivery flow rate. Note: High Flow Oxygen will only be documented when using a high flow oxygen delivery device that warms and humidifies the oxygen.

The Sponsor will derive the O2 saturation/FiO2 ratio, using accepted standards for converting O2 delivery rates to FiO2 values.

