2.3 Study Endpoints and Evaluations

Primary Endpoint

- Proportion of patients who have died or progressed to RF as defined by progressing to the need for high-flow nasal cannula O₂ delivery, noninvasive positive pressure ventilation, invasive mechanical ventilation, or extracorporeal membrane oxygenation (ECMO) therapy by Day 28.

Secondary Endpoints

1. Safety as assessed by AEs as measured by the Common Terminology Criteria for Adverse Events (CTCAE) v 5.0
2. Proportion of patients surviving [Time Frame: at Day 14, at Day 28, at Day 57]
3. Proportion of subjects who survive without progression to RF [Time Frame: at Day 14, at Day 28, at Day 57]

QMS Document Name: Statistical Analysis Plan	Page 9 of 27
QMS No (include version ref): STF-015-GL.02	Document date: 09JUL2019
CONFIDENTIAL	

4. Time to two successive negative viral titers in nasopharyngeal swab
5. Time to clinical worsening from baseline value (defined by time to ≥ 1 -point worsening on WHO Ordinal Scale for COVID-19):

World Health Organization Ordinal Scale for COVID-19

Patient State	Description	Score
Uninfected	No clinical or virological evidence of infection	0
Ambulatory	No limitation of activities	1
	Limitation of activities	2
Hospitalized, Mild Disease	Hospitalized, no oxygen therapy	3
	Oxygen by mask or nasal prongs	4
Hospitalized, Severe Disease	Noninvasive ventilation or high-flow oxygen	5
	Intubation and mechanical ventilation	6
	Ventilation + additional organ support – pressors, RRT, ECMO	7
Dead	Death	8

Abbreviations: ECMO = extracorporeal membrane oxygenation; RRT = renal replacement therapy

6. Proportion of patients who develop critical COVID-19 illness as defined by at least one the following:
 - A. Respiratory failure defined based on resource utilization requiring at least one of the following: Endotracheal intubation and mechanical ventilation, oxygen delivered by high-flow nasal cannula (heated, humidified, oxygen delivered via reinforced nasal cannula at flow rates > 20 L/min with fraction of delivered oxygen ≥ 0.5), noninvasive positive pressure ventilation, ECMO clinical diagnosis respiratory failure (i.e., clinical need for one of the preceding therapies, but preceding therapies not able to be administered in setting of resource limitation)
 - B. Hemodynamic compromise (defined by systolic blood pressure < 90 mm Hg, or diastolic blood pressure < 60 mm Hg or requiring vasopressors)
 - C. Multi-organ dysfunction/failure

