4.2 Covariates and Strata

The primary endpoint (proportion who have died or progressed to RF at 28) will be analyzed using a logistic regression with treatment group and covariates, age group (50 to < 75 years, and \geq 75 years), and region. Other covariates including previous COVID-19 therapy may be explored as exploratory analyses.

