10.2.4 Other continuous secondary efficacy endpoints

Following continuous endpoints will be analyzed using an analysis of covariance (ANCOVA) model, with treatment as a fixed effect and baseline WHO Ordinal Scale score, age group (50 to < 75 vs. ≥ 75 years of age) and region. Results from Wilcoxon rank sum test and t-tests will also be reported. The ITT and PP analysis (if formed) sets will be used for these exploratory subset analyses.

- Duration of intubation: which will be defined as duration of first post-dosing intubation based on start and end date of the intubation.

QMS Document Name: Statistical Analysis Plan	Page 21 of 27
QMS No (include version ref): STF-015-GL.02	Document date: 09JUL2019
CONFIDENTIAL	

- Length of intensive care unit (ICU) stay in days which will be defined as duration of first post-dosing ICU stay based on start and end date/time of the stay.
- Duration of supplemental O₂ administration in days : which will be defined as duration of first post-dosing supplemental O₂ administration based on start and end date/ of the O₂ administration.
- Duration of noninvasive ventilation or high-flow oxygen therapy in days: which will be defined as duration of first post-dosing noninvasive ventilation or high-flow oxygen therapy based on start and end date/time of the noninvasive ventilation or high-flow oxygen therapy.
- Duration of mechanical ventilation in days: which will be defined as duration of first post-dosing mechanical ventilation based on start and end date/time of the mechanical ventilation.
- Duration of mechanical ventilation plus additional organ support using vasopressors, and/or renal replacement therapy and/or ECMO: which will be defined as duration of first post-dosing mechanical ventilation plus additional organ support using vasopressors, and/or renal replacement therapy and/or ECMO based on start and end date/time of the mechanical ventilation plus additional organ support using vasopressors, and/or renal replacement therapy and/or ECMO.
- Daily ratio of oxygen saturation (SpO₂) to fractional inspired O₂ (SpO₂/FiO₂): which will be defined as SpO₂/FiO₂ as collected in CRF. The ratio will be analyzed for each day with the value being collected. If FiO₂ was not collected for some O₂ delivery methods, following guide can be followed to convert O₂ flow rate to FiO₂.

O ₂ delivery method	O ₂ flow rate (l/min)	Estimated FiO ₂
Nasal cannula ("NASAL CANNULA LARGE TUBING" and "NASAL CANNULA TRADITIONAL TUBING")	1	24
	2	28

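### The primary logistic model omits baseline SpO2/FiO2, a scheduled and probably prognostic measure, at a modest cost in efficiency

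*SAP*

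**What the plan says.** SAP 4.2 and 10.1 define the primary model as treatment plus two covariates: "The predefined covariates are region and age group". Age is split at 75 years. The PROC LOGISTIC code in 10.1 has the same terms. Anything further is optional: "Other covariates including previous COVID-19 therapy may be explored as exploratory analyses". SpO2/FiO2 is not named.

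The endpoint in SAP 2.3 is "Proportion of patients who have died or progressed to RF as defined by progressing to the need for high-flow nasal cannula", noninvasive or invasive ventilation, or ECMO.

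Protocol 7.2.6 says that the O2 saturation/FiO2 "ratio will be collected on the study days as specified in" Table 1, which lists screening, Day 1 and each treatment day. SAP 4.7 defines baseline as the last non-missing value before randomization. Where a device gives no FiO2 reading, SAP 10.2.4 says that the "following guide can be followed to convert" flow rate to FiO2. The ratio is used as a daily secondary endpoint ("The ratio will be analyzed for each day with the value being collected") and in the vital-signs summaries of SAP 11.3.

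Protocol 8.4 also had baseline WHO score (3 or 4) in the primary model. SAP v5.0 removed it. The addendum explains that blinded review found no RF among subjects with a baseline score of 3, which produces quasi-complete separation. No other severity term took its place.

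**The concern.** The endpoint is largely a step up in oxygen support, so a subject's starting oxygen need should be a strong predictor of it. The addendum points the same way, since no subject without oxygen at baseline had RF.

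No model in either document grades severity among subjects already on oxygen. WHO score 4 is the single category "Oxygen by mask or nasal prongs". In the SAP's own table it spans an estimated FiO2 of 24% (cannula, 1 L/min) to 60% (simple mask), and up to 100% with a reservoir mask.

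Leaving out a strong baseline predictor gives up power that costs nothing to collect. It also leaves chance imbalance in starting oxygen need unadjusted. Both matter more in a smaller trial, and the addendum says that enrollment stopped before the interim analysis.

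**Working it through.** **1. Planned sample size.** Inputs from Protocol 8.6: 31% vs 15%, two-sided 5%, 90% power, 1:1. The mean rate is 0.23 and the difference d is 0.16.

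- n = [1.960·√(2·0.23·0.77) + 1.2816·√(0.31·0.69 + 0.15·0.85)]² / 0.16² = (1.1665 + 0.7488)² / 0.0256 = 143.3.
- Continuity correction: (n/4)·[1 + √(1 + 4/(n·d))]² = 35.82·(1 + √1.1745)² = 155.5, so 156 per arm and 312 in total.

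This matches the plan. Full enumeration of Fisher's exact test at 156 per arm gives power 0.905.

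**2. Spread within WHO score 4.** Take SpO2 of 92% as an illustration, with FiO2 from SAP 10.2.4: 92/0.24 = 383, 92/0.60 = 153, 92/1.00 = 92. These are possible values, not the enrolled distribution.

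**3. Does the addendum's separation problem carry over?** Not automatically. Room air at 85% gives 85/0.21 = 405. A 1 L/min cannula at 97% gives 97/0.24 = 404. Values from scores 3 and 4 can overlap, so a continuous term has no empty cell.

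**4. Power for the odds-ratio test.** Simulated model: logit P(event) = a(arm) + β·X, with X standard normal. The arm intercepts are set so that the marginal rates are 31% and 15%. Both fitted models contain treatment, region and age group, and one adds X. Region and age are simulated as non-prognostic. Gain in effective sample size = (mean adjusted z / mean unadjusted z)² − 1. The odds ratio per SD, exp(β), is an assumption.

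| OR per SD | Gain in effective N | Power, 156 per arm | Power, 75 per arm |
|---|---|---|---|
| 1.5 | about 2-3% | 0.926 to 0.930 | 0.636 to 0.646 |
| 2.0 | about 7% | 0.927 to 0.941 | 0.636 to 0.670 |
| 2.5 | about 11% | 0.925 to 0.947 | 0.639 to 0.696 |

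The gains are 0.4, 1.4 and 2.2 points at 156 per arm, and 1.0, 3.4 and 5.7 points at 75 per arm. Simulation error is a few tenths of a point or more. Repeat runs put the top gain at 156 per arm as high as 2.6 points. A repeat of the last 75-per-arm setting (8,000 replicates) gave 0.646 to 0.697, so about 5 points is a fair reading there.

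**5. Precision.** A separate simulation (4,000 trials per setting, one covariate against none) gave the variance of the standardized risk difference at N = 312:

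| Control-arm AUC | OR per SD | Variance ratio | Equivalent N |
|---|---|---|---|
| 0.60 | exp(0.36) = 1.43 | 0.988 | 308 |
| 0.65 | exp(0.56) = 1.75 | 0.945 | 295 |
| 0.70 | exp(0.79) = 2.20 | 0.905 | 282 |

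At an illustrative N of 200, power rose from 0.784 to 0.788, 0.770 to 0.794 and 0.769 to 0.802.

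The standard error of the log odds ratio goes the other way. At AUC 0.70 and N = 312 it rises from 0.286 to 0.304, because the conditional odds ratio lies further from 1 (0.357 against 0.393 with no covariate effect). For the test, the benefit is power.

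**6. Robustness.** Adding measurement error with SD 0.5 to X, to mimic flow-estimated FiO2, left gains of about 5% and 9% at OR 2.0 and 2.5. Type I error with the covariate was 0.053 at 75 per arm and 0.051 at 100 per arm.

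**The case against.** The best defence is that nothing is wrong with the current model. It adjusts for both stratification factors, and neither bias nor inflated type I error is shown. That stands, and it sets the weight of this point. A reader might infer that the primary result would be biased, or that the odds ratio is estimated less precisely. The documents support neither. The unadjusted odds ratio is a different, marginal quantity, and its standard error is the smaller one.

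The size of the benefit is assumed. Neither document gives the prognostic strength of SpO2/FiO2 or the enrolled N. At OR 1.5 and 156 per arm the gain is negligible. This also stands.

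The simulated covariate is idealized. The real ratio is partly estimated (cannula flow is capped at 44% from 6 L/min), and room-air subjects will cluster near the top of the scale. Step 6 covers measurement error, but clustering is not quantified.

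The choice would come late. All subjects had passed Day 28, and blinded review had already related pooled outcomes to baseline oxygen status. That is a real but small drawback: without treatment codes, the choice cannot be steered towards an arm, provided that it is fixed before unblinding.

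The SAP does allow exploratory covariates, a baseline WHO subgroup and summaries of SpO2/FiO2 by arm. These would show an imbalance, but they do not adjust the primary test for it.

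A reader might also infer that dropping the WHO score was a mistake. That is a separate question, and the addendum gives a reason for it.

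**Conclusion.** The point holds as an avoidable loss of efficiency. A predictor that is scheduled for all subjects, with baseline and conversion rules already written, is missing from the primary model. The cost is some power for the odds-ratio test and some precision for the adjusted risk difference.

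With an assumed odds ratio per SD of 1.5 to 2.5, effective sample size would rise by about 2-3% to 11%. That is about 0.4 to 2 power points at 156 per arm and about 1 to 5 points at an illustrative 75 to 100 per arm. If the ratio is only weakly prognostic, the gain is close to nil.

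The addendum's finding for WHO score 3 supports prognostic relevance but does not measure it. Scheduled for everyone also does not mean observed in everyone.

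**What to change.** Before unblinding, and through the protocol amendment that SAP section 1 requires for changes to the primary analysis:

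- Add continuous baseline SpO2/FiO2 to the primary logistic model in SAP 4.2 and 10.1. Use the last pre-randomization value, with FiO2 from the device or the SAP 10.2.4 table. Set a missing baseline to the pooled median.
- Carry it into the logistic-based risk difference (the published covariate-adjustment method that SAP 10.1 cites), the multiple-imputation and analysis models in 10.1 with their code, and the Cox model that uses the same covariates.
- Leave the CMH-weighted estimate on region and age strata, since a continuous ratio does not define strata.
- Keep the region-and-age model as a named sensitivity analysis.
- State whether the binary secondary endpoints in 10.2.1, which follow the primary analysis, inherit the covariate.

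No new data are needed. The cost is an amendment, edits to several models and their code, and two small drawbacks to disclose: FiO2 is estimated for some devices, and the covariate is specified late, after blinded review of pooled outcomes.

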2.2 Sample Size Determination

The sample size estimate of 312 total subjects is based on 31% progressing to RF by Day 28 in the placebo group and 15% progressing to RF in the asapirant group using data from recently published COVID-19 studies (Guimaraes et al 2021, Temesgen et al, 2021). Using a Fishers Exact test with two-sided 5% Type 1 error and 90% power, the sample size to detect a 16% absolute improvement in the primary endpoint is 312 patients (1:1 randomization). Randomization will be stratified based on the patient's enrollment region (North America vs. South America) and age (50 to < 75 vs. ≥ 75 years of age).

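### The multiple imputation ignores event-free time up to last contact, so it over-imputes failures; the effect is small with equal loss and becomes a bias when loss differs by arm

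*SAP*

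**What the plan says.** SAP 10.1 applies multiple imputation "If more than 5% of subjects have insufficient data to confirm RF-free and alive at Day 28". It assumes "missing at random (MAR) based protocol stratification factors (age and region), treatment, and the discharge status prior to or on Day 28". The imputed variable is cumulative from the start of the study: "RF28 is respiratory failure or death prior to or on Day 28". The predictors are those in the Step 1 code, "VAR TRT01P REGION AGEGRN DISC28 RF28": arm, region, age group and one discharge flag covering the whole 28 days. Neither the day of last contact nor the status on that day enters the model.

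The same section uses the last-contact date in the time-to-event analysis of this endpoint: "For subject who discontinued study before Day 28 without documented outcome, it will be censored at the date of discontinuation". Protocol 8.4 ties the imputation to the patient's last known status and gives the last WHO score as an example. The SAP replaces this with the discharge flag, and SAP section 1 says that the SAP prevails.

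**The concern.** Documented RF or death before loss already makes RF28 a failure. RF28 can therefore be missing only for a subject with no documented event up to last contact. Step 1 does not use this. It fits one logistic model to all subjects with a known outcome, including those whose RF came before they went home. A subject discharged RF-free on Day 6 and then lost receives the 28-day risk of everyone discharged by Day 28, although most failures in that group had happened before discharge.

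Adding the last WHO score would not cure this. A subject who recovered from RF and was discharged can have the same last score as one who never failed.

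Above the 5% trigger this is the specified handling of the primary endpoint. The four success/failure sensitivity analyses in SAP 10.1 are attached only to the branch with 5% or less missing, so no alternative imputation is specified that would show the error.

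**Working it through.** **Plan's own figure.** SAP 2.2 sizes the trial "based on 31% progressing to RF by Day 28 in the placebo group and 15% progressing to RF in the asapirant group". It adds: "Using a Fishers Exact test with two-sided 5% Type 1 error and 90% power". With p̄ = 0.23, n per arm = [1.960·√(2·0.23·0.77) + 1.282·√(0.31·0.69 + 0.15·0.85)]² / 0.16² = 143.3. The continuity correction gives 143.3/4·[1 + √(1 + 4/(143.3·0.16))]² = 155.5, so 156 per arm and 312 in total, as stated. The planned rates can be used as inputs.

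**Assumptions not in the documents.** A fraction d = 0.30–0.60 of failures and 97% of non-failures are discharged by Day 28. All losses follow RF-free discharge, 2% of lost subjects truly fail, and a fraction L of each arm is lost.

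**Imputed risk for a lost, discharged subject.** Among observed subjects discharged by Day 28:

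risk = (p·d − 0.02L) / [p·d + 0.97(1 − p) − L]

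At L = 0.10:
- Placebo, d = 0.30: (0.093 − 0.002)/(0.093 + 0.6693 − 0.10) = 13.7%. At d = 0.60: 0.184/0.7553 = 24.4%.
- Asapiprant, d = 0.30: 0.043/0.7695 = 5.6%. At d = 0.60: 0.088/0.8145 = 10.8%.

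The assumed true risk is 2%. Fitting the main-effects logistic model that the SAP specifies, instead of arm-specific proportions, changes these by 0.1 point or less.

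**Effect on the comparison.** Imputed arm rate = p − 0.02L + L·risk. The true difference is 16.0 points and the true odds ratio is (0.15/0.85)/(0.31/0.69) = 0.393.

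| True rates | Lost, placebo / asapiprant | Imputed rates, d = 0.30 | Imputed rates, d = 0.60 | Difference (points) | Odds ratio |
|---|---|---|---|---|---|
| 31% / 15% | 10% / 10% | 32.2 / 15.4 | 33.2 / 15.9 | 16.8–17.4 | 0.38 |
| 31% / 15% | 14% / 4% | 32.8 / 15.1 | 34.3 / 15.3 | 17.6–19.0 | 0.35–0.37 |
| 31% / 31% | 10% / 10% | 32.2 / 32.2 | 33.2 / 33.2 | 0 | 1.00 |
| 31% / 31% | 4% / 14% | 31.4 / 32.7 | 31.8 / 34.3 | −1.3 to −2.5 | 1.06–1.12 |

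**Simulation check.** 156 per arm, 800 trials per scenario and 25 imputations, with arm and discharge in the model. Assumed timing: median RF onset Day 4, RF-free discharge around Day 7–8, 5% of failures after discharge, half of RF subjects discharged, about 9% missing.
- Equal post-discharge loss, 31% vs 15%: mean difference 0.162 with complete data, 0.169 with Step 1, 0.162 with residual-risk imputation. Power was 93.6%, 93.4% and 93.6%.
- Equal post-discharge loss, 23% in both arms: no bias; rejection 5.6%, 6.0% and 5.8%.
- Post-discharge loss about 5% placebo vs 13% asapiprant, 31% vs 15%: power 90.9%, 86.9% and 90.7%. Under the null, Step 1 was 1 point off zero and rejection was 5.0% with all three methods.

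**In-hospital withdrawals.** Their discharge status to Day 28 is unobserved. If the flag were set to not discharged, the imputed risk would be p(1 − d)/[p(1 − d) + 0.03(1 − p)]. That is 86–91% on placebo and 70–80% on asapiprant.

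**The case against.** - **The effect on the test is small when loss is balanced.** Step 3 pools logistic coefficients, not a risk difference, so the odds ratio is the relevant scale. It barely moves with equal post-discharge loss, and the null is preserved. This stands.
- **Large distortions depend on an unstated coding.** A reader might infer serious type I error inflation. In the simulation, unequal in-hospital withdrawal moved the null difference by 5–6 points and gave 15–19% rejection. Those runs code withdrawn inpatients as not discharged, which the SAP does not specify. It does provide for imputing missing covariates. Doing so for the flag would give roughly the arm averages, 31% and 15%: still above residual risk except for very early losses, but far from 70–90%. The documents do not support the larger figures as a prediction.
- **Event-free status is not always certain.** The trigger is insufficient data, and after discharge the WHO scale is specified only at Day 14 and follow-up visits. The accurate statement is that no event is documented up to last contact. If sicker subjects drop out selectively, part of the over-imputation is offset; the SAP, however, assumes MAR.
- **Protocol 8.4's default of counting missing as failure over-imputes more.** True, but that is an open, fixed rule. Step 1 is presented as a MAR estimate while leaving out the observed history on which MAR should condition.
- **The time-to-event analysis already uses the event-free time.** It does. Different assumptions across analyses are not in themselves a contradiction. But it does not correct the primary analysis.

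**Conclusion.** The mechanism follows from the SAP text: above 5% missing, Step 1 gives subjects failure risk for days already passed without a documented event, and under MAR it over-imputes failures. The size is conditional, because neither document gives a dropout rate, discharge rates or event timing.

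Under the assumptions above, imputed risk after discharge is several times the true 2%. With equal loss the treatment comparison hardly changes. With unequal loss the bias runs against the arm that loses more subjects. In the 4% vs 14% null scenario, a separate simulation of 1,500 trials gave 6.2% rejection, against 4.8% with conditional imputation. That is a modest excess, given a Monte Carlo standard error of about 0.6 points.

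It would go too far to conclude that the trial's result must be materially distorted. That needs clearly unequal loss, or a coding of in-hospital withdrawals that the SAP leaves open. The SAP addendum also reports that enrolment stopped before the interim analysis, so 156 per arm probably does not describe the final data and the simulated power and rejection rates are illustrative. The correction is worth making because it is cheap and uses data already collected.

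**What to change.** Replace Step 1 with imputation conditional on being alive and RF-free at last contact and on status that day (in hospital or discharged). Either of two forms would do:

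1. Split the time to Day 28 into a few intervals. In each, fit the logistic model only among subjects still event-free at its start, using discharge status at that point in place of the 28-day flag. Impute forward from each subject's last contact. Late events are few, so limit covariates or pool the late intervals; the addendum already reports quasi-complete separation for one covariate.
2. Draw from the Kaplan-Meier residual risk within arm and discharge status. Using arm alone is not equivalent. If RF onset is exponential with a median of 4 days, the fraction of failures still to come at Day 6 is 2^(−6/4) = 0.354. The residual risk is then 0.31·0.354/(0.31·0.354 + 0.69) = 13.7% on placebo and 0.15·0.354/(0.15·0.354 + 0.85) = 5.9% on asapiprant, against an assumed 2% for discharged subjects.

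Both forms use discharge status at last contact, so the coding question for in-hospital withdrawals disappears. Steps 2 and 3 stay as they are. The cost is SAP wording and programming, with less stable models in the late intervals. No new data are needed. The change should be settled before unblinding.
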